6.2 Screen Failure

A subject will be considered a screen failure if written informed consent is obtained but he/she does not meet inclusion / exclusion criteria or does not receive SUBLOCADE for another reason (example: the subject leaves prior to administration).

Subjects that screen fail may be re-screened for participation in the trial if they return to the ED, inpatient unit or outpatient treatment facility after a subsequent OD.

6.3 Subject Completion

6.3.1 Treatment Completion

Subjects that complete the EOT visit will be considered treatment completers.

6.4 Withdrawal and Stopping Criteria

6.4.1 Subject Withdrawal from Treatment

A subject will be considered withdrawn from treatment if the subject has permanently discontinued study treatment. The primary reason for withdrawal from treatment must be entered into the electronic case report form (eCRF) (e.g., death, AE, protocol non-compliance, investigator's decision, or as requested by the subject for another or unknown reason). Subjects who discontinue study treatment for any reason other than lost to follow-up will continue to be followed on an approximately monthly basis by telephone for repeat OD and treatment status and any scheduled HEOR assessments through to the end of their scheduled 30-day safety follow up telephone call.

Subjects who are withdrawn from the study for any reason after treatment with SUBLOCADE will not be replaced.

6.4.2 Subject Withdrawal from the Study

If the subject has permanently discontinued study treatment and monthly follow-up calls, he/she will be considered withdrawn from the study. The primary reason for withdrawing from the study must be entered into the eCRF (e.g., subject is lost to follow-up, or investigator's discretion).

Female subjects with confirmed pregnancies will be withdrawn from the study. See Protocol [Section 12.2](#) for additional information.

6.4.3 Subject Withdrawal of Consent

If a subject withdraws consent, the primary reason should be entered into the eCRF. The subject will not receive any additional doses of study treatment. However, the subject may be offered additional tests as needed to monitor their safety (e.g., EOT safety assessments or procedures).

6.4.4 Subjects Lost to Follow-up

In cases of a missed visit, the Investigator or designee must attempt to contact the subject and re-schedule as soon as possible. The Investigator or designee must counsel the subject on the importance of maintaining the assigned visit schedule and ascertain whether or not the subject wishes to and/or should continue in the study.

In the event a subject misses 5 consecutive weeks' worth of visits, they will be considered to have ceased treatment and withdrawn from the study. Investigators or designees must make a reasonable effort to contact the subject. Two documented attempts (e.g., phone, email, etc.) to contact the subject followed by a certified mailed letter is considered reasonable. Subjects who can no longer be contacted will be considered lost to follow-up.

For the purpose of documenting date of discontinuation for a subject confirmed to be lost to follow-up, the date of discontinuation will be the date of last in-person visit.

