3 STUDY ENDPOINTS

3.1 Primary

The primary endpoint of this study is:

- Time to repeat OD or opioid-related death. Repeat OD or opioid-related death will be measured from electronic medical records and state death registries.
- Additional comparisons on repeat OD and death rates will be made to concurrent patients who decline to participate in the SUBLOCADE injection.

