14.7 Efficacy Analysis

14.7.1 Primary Efficacy Analysis

The repeat opioid OD or opioid-related death primary endpoint analysis will be performed using Cox proportional regression and compare the SUBLOCADE treatment arm to historical and concurrent control data. Propensity scores will be used to match study participants to controls. Repeat OD and deaths (measured as time-to-event or censored at 6 months post index OD) will be tracked using subject reports, electronic medical records and state death registries. Events will be counted within the 6 months of treatment period for all treated subjects.

Propensity score analysis will be used in the analysis of SUBLOCADE vs. the control for time to repeat OD or opioid-related death. Study subjects will receive a propensity score that will be matched to propensity scores in the control data. The propensity score, p , will also be used as a weight in the Cox proportional hazards model. All SUBLOCADE treatment group subjects will have a weight of $p=1$ and patients in the control groups will be weighted by $p/(1-p)$. Here p can be viewed as the probability that the control subject would have been a study participant if the study were performed during their treatment.

The propensity score will be estimated by fitting a logistic regression on a dataset consisting of the consenting subjects (subjects in the SUBLOCADE arm at VCU) and the controls. The response variable will be consent to treatment; predictors will include baseline characteristics such as subject age, gender, county, race and insurance status. This model will be used to generate the predicted probability of consent to participate among the controls.

The Cox proportional hazards model will use the controls as the reference group and code the SUBLOCADE arm as a factor variable. The analysis will test the coefficient for the SUBLOCADE arm versus the controls from the Cox regression, with the interpretation of the exponential (coefficient) as the hazard ratio for time to repeat OD or opioid-related death in subjects consenting to the active treatment group versus the control cohorts.

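### The five-week missed-visit rule in 6.4.4 and 10.1.1 withdraws reachable subjects from the study, contradicting 6.4.1 and 6.4.2 and ending their telephone follow-up for repeat overdose

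*Combined protocol and SAP*

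**What the plan says.** Four sections of the protocol decide what happens to a subject who stops attending.

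- **6.4.4, repeated in 10.1.1.** After five weeks of missed visits, subjects fall under this rule: "they will be considered to have ceased treatment and withdrawn from the study". The site then makes two documented contact attempts and sends a certified letter. Lost to follow-up is a separate, later status: "Subjects who can no longer be contacted will be considered lost to follow-up". For subjects confirmed as lost, "the date of discontinuation will be the date of last in-person visit".
- **6.4.1.** "Subjects who discontinue study treatment for any reason other than lost to follow-up" stay under observation: they "will continue to be followed on an approximately monthly basis by telephone for repeat OD and treatment status", and for scheduled HEOR assessments, up to the 30-day safety call.
- **6.4.2.** "If the subject has permanently discontinued study treatment and monthly follow-up calls, he/she will be considered withdrawn from the study".
- **14.7.1.** "Events will be counted within the 6 months of treatment period for all treated subjects". Follow-up is censored at 6 months after the index overdose, and the sources are subject reports, electronic medical records and death registries.

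The endpoint definition in 3.1 names two of those sources: "Repeat OD or opioid-related death will be measured from electronic medical records and state death registries". Section 3.6 again includes self-report.

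**The concern.** A subject who misses five weeks of visits but answers the telephone is kept in the calls by 6.4.1 and removed from the study by 6.4.4. Site staff cannot do both. Because the withdrawal wording appears twice, it is unlikely to be a slip that staff will ignore.

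If 6.4.4 prevails, the subject loses telephone follow-up for repeat overdose, treatment status, HEOR and, on the natural reading of 10.1.1, serious adverse events. The overdose loss matters most, because 14.7.1 relies on subject report for the primary endpoint. The study's third entry route recruits people treated by EMS who declined transport to an ED. A repeat overdose of that kind, or one treated at another hospital, may leave no trace in the VCU record and, if not fatal, none in a death registry. Attenders can report such an event at a visit, and subjects who formally stop treatment can report it by telephone. Five-week non-attenders can do neither.

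**Working it through.** **1. The rules side by side, by type of subject**

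| Subject | 6.4.1 | 6.4.2 | 6.4.4 / 10.1.1 | Conflict? |
|---|---|---|---|---|
| Stops treatment, says so, reachable | Calls continue | Not withdrawn while calls continue | Not triggered | No |
| Misses five weeks, reachable | Calls continue | Not withdrawn while calls continue | Withdrawn from the study | **Yes** |
| Misses five weeks, cannot be contacted | Excluded from calls | Withdrawn, since treatment and calls have ended | Withdrawn, lost to follow-up | No |

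The conflict is confined to the middle row.

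**2. What each source still captures for that subject**

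- Medical records at VCU: need no visit or call. Planned for all treated subjects.
- Death registries: the same.
- Subject report (3.6, 14.7.1): stops if 6.4.4 is followed.

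No section says whether records and registry follow-up continues after withdrawal from the study. The wording of 14.7.1 and the treatment population in 14.4.1 (at least one dose, no exclusion for withdrawal) imply that it does.

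**3. The plan's own figure**

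Inputs from 14.2: 99 treated, 198 historical controls, 3% versus 11.5% at 6 months, type I error 5%, stated power 80%. A one-sided Fisher exact test at 0.05 gives 80.25%, which reproduces the stated figure (the two-sided version gives 73.0%). The calculation contains no allowance for missed events, and nothing in this point changes it.

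**4. How many treated events are at stake**

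- Expected treated events: 0.03 × 99 = 2.97, about 3.
- Expected control events: 0.115 × 198 = 22.77.
- Share of planned treated events that one missed event represents: 1 / 2.97 = 34%.
- Effect on the observed treated rate: 3/99 = 3.0% becomes 2/99 = 2.0%.

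The expected number missed is 2.97 × (share of treated events that occur in reachable non-attenders after the rule applies) × (share of those known only by subject report). The documents give neither share, so the product cannot be narrowed.

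**5. How much telephone follow-up is lost**

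The longest case is a subject last seen on Day 1. The rule applies at about Day 1 + 35 = Day 36. Reading the end of the 6.4.1 calls as the Day 199 safety call in Appendix 2, 199 − 36 = 163 days remain, and 163 / 30 ≈ 5.4, or about five monthly calls.

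**The case against.** The strongest reply is that the primary endpoint does not depend on these calls. Section 3.1 measures it from records and registries, and 14.7.1 counts events in every treated subject to 6 months. That stands: non-attenders lose one of three sources, and under 3.1 read alone the endpoint loses nothing. But 3.6 and 14.7.1 both name self-report, so the plan does intend to use it.

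It can also be said that 6.4.4 is headed as a rule on subjects lost to follow-up, so its authors may have had only unreachable people in mind. That is a plausible intent. The text nevertheless withdraws the subject first and makes lost to follow-up depend on failed contact afterwards.

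A reader might go further and infer that dropouts are censored at their last visit, which would be informative and would favour SUBLOCADE. The documents do not support this. Section 14.7.1 censors at 6 months after the index overdose. The last-visit date in 6.4.4 documents discontinuation for confirmed lost subjects, and the one in 14.8 serves the attendance endpoint. Any figure for that bias would rest on assumed dropout and hazards under a rule that the plan does not adopt.

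Nor does losing the calls by itself tilt the comparison. Concurrent controls are followed passively and historical controls come from a records extract, so neither group ever had calls. Finally, it is plausible that people who stop attending are at higher risk, but the documents do not quantify it.

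**Conclusion.** The contradiction is real and limited to subjects who miss five weeks of visits but can still be contacted. For them, following 6.4.4 and 10.1.1 discards follow-up that 6.4.1 promises. Ascertainment of repeat overdose within the treated arm then varies with attendance. With about 3 treated events planned, one unreported overdose is roughly a third of the total. That scale assumes the 3% rate in 14.2. How many events would be missed cannot be derived from the documents.

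Records and registry capture and the 6-month censoring rule are intact on their face, so this point claims no size or direction of bias in the comparison with controls. The remaining gap is silence: the plan does not say that records follow-up outlasts study withdrawal, or that the last-visit dates stay out of the primary dataset. The correction should be made because sites cannot follow both rules and the remedy is cheap.

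**What to change.** 1. In 6.4.4 and 10.1.1, replace "they will be considered to have ceased treatment and withdrawn from the study" with wording under which the subject is considered to have ceased treatment only. This leaves untouched the point at which treatment is regarded as stopped.
2. In the same sections, state that subjects who can be contacted move to the 6.4.1 monthly calls, and reserve study withdrawal for the 6.4.2 definition.
3. In 14.7.1, state that records and registry follow-up runs to 6 months after the index overdose for all treated subjects unless consent is withdrawn, and that the last-visit dates in 6.4.4 and 14.8 are not censoring dates for the primary endpoint.

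Two neighbouring inconsistencies should be reconciled in the same amendment. Section 6.4.4 counts five weeks where 14.8 counts five visits, and these diverge once visits become two-weekly after Week 14. On confirmed pregnancy, 6.4.2 withdraws the subject from the study, while 12.2 withdraws her from treatment and continues the calls.

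The cost is wording plus, on the count above, up to about five calls for each reachable non-attender. The calls are already planned. One limitation remains: subject report is a source that the controls lack, whichever rule is followed.

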6.4.5 Liver Chemistry Stopping Criteria

Liver chemistry stopping criteria 1-5 are defined below:

1. The subject has ALT or AST $>3 \times$ ULN **and** bilirubin $>2 \times$ ULN ($>35\%$ direct bilirubin) (or ALT or AST $>3 \times$ ULN **and** international normalized ratio (INR) >1.5 , if INR measured).
Note: if serum bilirubin fractionation is not immediately available, withdraw study drug for that subject if ALT or AST $>3 \times$ ULN and bilirubin $>2 \times$ ULN. Serum bilirubin fractionation should be performed if testing is available. If testing is unavailable, the presence of detectable urinary bilirubin on dipstick should be recorded, indicating direct bilirubin elevations and suggesting liver injury.
2. The subject has ALT or AST $>8 \times$ ULN.
3. The subject has ALT or AST $>5 \times$ ULN but $<8 \times$ ULN persisting for > 2 weeks.

4. The subject has ALT or AST >3 x ULN if associated with symptoms (new or worsening) believed to be related to hepatitis (such as fatigue, nausea, vomiting, right upper quadrant pain or tenderness or jaundice) or hypersensitivity (such as fever, rash, or eosinophilia).
5. The subject has ALT or AST >5 x ULN but <8 x ULN and cannot be monitored weekly for >2 weeks.

6.4.5.1 Study Treatment Re-challenge

Study treatment re-challenge after liver chemistry stopping criteria are met by any study subject is not allowed. If clinically indicated, the SUBLOCADE depot may be surgically removed within 14 days of the injection.

7 STUDY SUSPENSION OR TERMINATION

In cases where a trial is suspended or terminated for safety reasons, the Principal Investigator (PI) will promptly inform the Regulatory Authorities of this action and the reason(s) for the suspension or termination.

If required by applicable regulations, the PI must inform the Institutional Review Board/Independent Ethics Committee (IRB/IEC) promptly and provide the reason(s) for the suspension or termination.

8 DESCRIPTION OF STUDY PROCEDURES

Study assessments and procedures, including the timing of assessments, are summarized in Appendix 1 and Appendix 2. Further details on efficacy assessments are provided in Section 8.6.

A signed written informed consent form must be obtained from the subject before any study assessments or procedures may be performed. At screening, if an assessment or procedure has already been performed as part of routine standard of care and was completed within the protocol-specific screening window, the assessment or procedure does not need to be repeated, unless clinically indicated. All assessments and procedures may be performed more frequently, if clinically indicated.

8.1 Demographics and Medical History

A detailed medical history will be obtained during the screening period. This will include information regarding the subject's complete history of relevant medical conditions, diagnoses, procedures, treatments, detailed history of drug use and any other noteworthy medical information. Any updates to medical history information made available during the course of the study will be captured.

8.1.1 DSM-5 Checklist for OUD, AUD and SUD and Mini-International Neuropsychiatric Interview (DSM 5 version)

At screening, the DSM-5 Checklist will be performed to assess for the presence and severity of OUD, AUD and SUD and will be reviewed by the PI or Sub-Investigator. At visit 2, the standardized diagnostic tool of the Mini-International Neuropsychiatric Interview (M.I.N.I), DSM-5 version (7.0.2) ([Sheehan, 2016](#)) will be used to screen for other DSM-5 substance-use disorders or other psychiatric co-morbidities.

8.2 Physical Examination

A brief physical examination will include an assessment of general appearance, lungs and cardiovascular system. The brief physical examination will occur in the ED, inpatient unit or at the clinic within 7 days (168 h) of the opioid OD at screening, and at the first clinic visit.

If any clinically significant change from screening is noted, it will be reported as an AE and followed up to resolution or until reaching a stable endpoint.

The Richmond Agitation-Sedation Scale (RASS) will be utilized to assess sedative effects of SUBLOCADE 300 mg in patients with COWS <8 and who were released from a controlled environment in the past 30 days (Sessler et al 2002). Patients with a RASS score > 0 will be eligible for discharge after a 2 hour wait period.

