The study will assess subjects that receive acute administration of SUBOXONE sublingual film followed by SUBLOCADE administration in the 1) ED, 2) inpatient unit or 3) within 7

days (168 h) after OD in an affiliated outpatient treatment clinic combined with 6 months of treatment with SUBLOCADE in the outpatient treatment clinic compared to historical and concurrent control data from VCU electronic health records. The affiliated clinic will agree to see the subject on arrival at the clinic during normal clinic hours.

Subjects will be given the opportunity to participate in an optional pharmacogenetics (PGx) sub-study.

- 1) Patients presenting to the ED for an opioid OD who received treatment with an opioid antagonist and are considered clinically stable and alert (respiratory rate [RR] \geq 12, pulse oximetry $>$ 95%, Glasgow Coma Scale [GCS] score of 15), and, who deny recent/regular use of long acting opioids (e.g., methadone) will be approached regarding interest in study participation. Written informed consent will only be obtained if the patient's judgement is intact as determined clinically by the Investigator or a medically qualified sub-investigator or research nurse. This OD will be considered the index OD.

Participants who meet inclusion/exclusion criteria will be administered 4 mg/1 mg SUBOXONE sublingual film in the ED followed by a 1-hour wait. If the subject displays no allergic/hypersensitivity reaction to SUBOXONE sublingual film after 1 hour, SUBLOCADE (300 mg) will be administered in the ED. Subjects will remain in the ED for 1 hour after the 300 mg SUBLOCADE injection and are clinically stable (respiratory rate [RR] \geq 12, pulse oximetry $>$ 95%, Glasgow Coma Scale [GCS] score of 15). A COWS assessment and AEs will be collected prior to SUBLOCADE administration and 1-hour post SUBLOCADE prior to discharge. Participants with initial COWS $<$ 8 and who were released from a controlled environment within the past 30 days, will remain in the ED for 2 hours after SUBLOCADE to assess for sedation using the Richmond Agitation-Sedation Scale. Patients will be discharged if RAS is 0 or greater. Patients who present with abnormal vital signs, or sign of sedation will remain in ED until they meet the ED discharge criteria. If participants experience precipitated withdrawal they will be treated symptomatically with medication as described in section 8.4 below.

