Participants who meet inclusion/exclusion criteria will be administered a 4 mg/1 mg SUBOXONE sublingual film followed by a 1-hour wait. If the participant displays no allergic/hypersensitivity reaction to SUBOXONE sublingual film after 1 hour, SUBLOCADE (300 mg) will be administered on the inpatient unit. Participants will remain in the inpatient unit for 1 hour after the 300 mg SUBLOCADE injection and are clinically stable (respiratory rate [RR] \geq 12, pulse oximetry $>$ 95%, Glasgow Coma Scale [GCS] score of 15. A COWS assessment and AEs will be collected prior to SUBLOCADE administration and 1-hour post SUBLOCADE. Participants with initial COWS $<$ 8 and who were released from a controlled environment within the past 30 days, will remain in the inpatient unit for 2 hours after 300 mg SUBLOCADE to assess for sedation using the Richmond Agitation-Sedation Scale. Patients will be discharged if RAS is 0 or greater. Patients who present with abnormal vital signs, or sign of sedation will remain in the inpatient unit. If participants experience precipitated withdrawal they will be treated symptomatically with medication as described in section 8.4 below.

Upon discharge, patients will be instructed to use over the counter ibuprofen and acetaminophen as needed. They will also be provided with two oral doses of 50 mg of hydroxyzine as ancillary medications if needed in the judgement of the clinician. The subject will receive referral to an outpatient treatment clinic affiliated with the hospital system in which the inpatient unit resides.

Patients presenting to the ED for an opioid OD who received treatment with an opioid antagonist, who are admitted to the inpatient unit and who are not approached by the study team for enrollment(e.g. discharge outside of regular business hours) will be given a referral card to go to the outpatient clinic by a healthcare provider for an initial screening visit. Subjects must arrive at the clinic within 7 days (168 h) of OD.

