- 3) Patients who are seen only by EMS personnel and are given an opioid antagonist for opioid OD but refuse transport to an Emergency Department but would like to be considered for the VOTIVE study will be given a referral card by EMS personnel. Patients who present to the ED or who are admitted to the inpatient unit for an Opioid OD and would like to be considered for the VOTIVE study but who are not approached by the study team (i.e. outside of business hours) will be given a referral card by a healthcare provider. The patient may present to the clinic within 7 days (168 h) of OD event for evaluation and initial screening visit.

In the clinic, subjects will be consented if they express interest in participating in the study. If participants meet study inclusion criteria and none of the exclusion criteria they will be administered 4 mg/1 mg SUBOXONE sublingual film followed by a 1-hour wait. If the subject displays no allergic/hypersensitivity reaction to SUBOXONE sublingual film after 1 hour, SUBLOCADE (300 mg) will be administered in the clinic. Subjects will remain in the clinic for 1 hour after the SUBLOCADE injection and are clinically stable (respiratory rate [RR] ≥ 12 , pulse oximetry $> 95\%$, Glasgow Coma Scale [GCS] score of 15. A COWS assessment and AEs will be collected prior to SUBLOCADE administration and 1-hour post SUBLOCADE prior to discharge. Participants with initial COWS < 8 and who were released from a controlled environment within the past 30 days, will remain in the outpatient clinic for 2 hours after 300 mg SUBLOCADE to assess for sedation using the Richmond Agitation-Sedation Scale. Patients will be discharged if RASS is 0 or greater. Patients who present with abnormal vital signs, or sign of sedation will remain in clinic or will be transferred to the ED until they are safe for discharge from the medical facility. If participants experience precipitated withdrawal, they will be treated symptomatically with medication as described in section 8.4 below.

Upon discharge, patients will be instructed to use over the counter ibuprofen and acetaminophen as needed. They will also be provided with two oral doses of 50 mg of hydroxyzine as ancillary medications if needed in the judgement of the clinician.

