1.2 Benefit-Risk Summary

Patients with OUD who survive an OD are at high risk of a subsequent OD. Treatment of OUD patients at high risk of OD (such as when released from incarceration), with methadone or buprenorphine reduces the risk of OD index cases by up to 85% (Marsden 2017). This supports treatment initiation as soon as possible after OD. The literature also supports a clear benefit of higher-dose MAT medications in patients at risk for opioid OD (Dupouy 2017, Marsden 2017, Sordo 2017). As noted above, SUBLOCADE at 300 mg administered subcutaneously on a monthly dosing regimen produces exposures at or above 2 ng/ml consistently, reaching higher exposures that appeared to be associated with improved outcomes. A potential advantage of using SUBLOCADE compared to transmucosal buprenorphine products in the emergency department (ED) following treatment for an opioid OD is the rapid achievement of plasma concentrations of 2 ng/ml buprenorphine which are sustained over the dosing interval. The risks associated with SUBLOCADE administered to patients with OUD in the ED are minimal, largely related to injection site reactions, precipitated withdrawal, or sedation which are significantly less than risk of repeat OD in this patient population.

Because there is a risk of sedation in patients who are not tolerant to opioid effects, patients who have a COWS of <8 and who were released from a controlled environment within the past 30 days will be observed for 2 hours after SUBLOCADE 300 mg administration and discharged with a RASS score > 0. This modification is intended to allow for enrolment of populations (i.e. patients who were recently incarcerated) that are especially vulnerable to opioid overdose due to a loss of opioid tolerance. Studies have shown that opioid overdoses are the leading cause of death in former prisoners in the immediate post-release period (Binswanger et al 2013).

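### The RASS score for discharge after the 2-hour observation is 0 or above in the synopsis but above 0 in Sections 1.2 and 8.2, so a score of exactly 0 is undecided

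*Combined protocol and SAP*

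**What the plan says.** Five places in the combined protocol and SAP give a RASS threshold for discharge. All five concern the same subgroup (COWS below 8 and recent release from a controlled setting) and the same 2-hour wait after SUBLOCADE 300 mg.

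- Synopsis, Study Design, ED pathway and inpatient pathway, in identical words: "Patients will be discharged if RAS is 0 or greater".
- Synopsis, Study Design, clinic pathway: "Patients will be discharged if RASS is 0 or greater".
- Section 1.2, Benefit-Risk Summary: these patients "will be observed for 2 hours after SUBLOCADE 300 mg administration and discharged with a RASS score > 0".
- Section 8.2, Physical Examination: "Patients with a RASS score > 0 will be eligible for discharge after a 2 hour wait period".

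Section 1.2 gives the reason for the check: "Because there is a risk of sedation in patients who are not tolerant to opioid effects".

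The synopsis has two further safeguards. It links the stay after injection to clinical stability (respiratory rate at least 12, pulse oximetry above 95%, Glasgow Coma Scale 15): "Subjects will remain in the ED for 1 hour after the 300 mg SUBLOCADE injection and are clinically stable" for the ED, "Participants will remain in the inpatient unit for 1 hour after the 300 mg SUBLOCADE injection and are clinically stable" for inpatients and "Subjects will remain in the clinic for 1 hour after the SUBLOCADE injection and are clinically stable" for the clinic. In each setting it also holds patients who have abnormal vital signs or show sedation.

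Appendix 1, footnote g, mentions the RASS score before discharge but gives no cut-off.

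**The concern.** The threshold decides when a subject who may have lost opioid tolerance can leave supervision after a long-acting dose. The protocol added the check so that this vulnerable group could be enrolled, so the threshold should have one value. As written, staff following the synopsis and staff following Section 8.2 could decide differently for the same subject with the same score.

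There is also a consequence for trial conduct. Section 8.11 requires every deviation to be addressed in the source documents. For a discharge at a score of 0, the text does not settle whether a deviation has occurred, so site staff and monitors could classify identical cases differently.

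**Working it through.** No figure in the plan has to be reproduced. The check is a comparison of the rules.

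**Step 1: do the statements cover the same situation?**

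| Place | Subgroup | Wait | Score for discharge |
|---|---|---|---|
| Synopsis, ED | COWS < 8 and release within 30 days | 2 hours | 0 or greater |
| Synopsis, inpatient unit | same | 2 hours | 0 or greater |
| Synopsis, clinic | same | 2 hours | 0 or greater |
| Section 1.2 | same | 2 hours | > 0 |
| Section 8.2 | same | 2 hours | > 0 |

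They do, so the difference cannot be explained as separate rules for separate cases. The ED and inpatient paragraphs abbreviate the scale as RAS, but the sentence just before names the Richmond Agitation-Sedation Scale in full, and the clinic paragraph writes RASS. It is one instrument.

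**Step 2: where do the rules differ?** Let s be the score. Rule A (synopsis) discharges if s ≥ 0. Rule B (Sections 1.2 and 8.2) discharges if s > 0.

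- s < 0: neither rule allows discharge, so they agree.
- s = 0: A allows discharge and B's condition is not met, so they conflict.
- s > 0: both allow discharge, so they agree.

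The set {s ≥ 0} without {s > 0} is {0}, which is one value. Listing the integer scores from −5 to 4 and from −10 to 10 gave the same single value. The result does not depend on the range of the scale, which the document does not state.

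**Step 3: does anything else settle a score of 0?** No order of precedence between the synopsis and the body is given. The Appendix 1 table has no RASS row, and its footnote g has no cut-off. The stability criteria and the sedation hold would keep some subjects in care whatever their RASS score, but the sedation hold is not tied to any RASS value. The case left open is therefore a subject in this subgroup who scores exactly 0, is clinically stable and shows no sedation.

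**Step 4: how many subjects?** The document gives neither the size of the subgroup nor the distribution of scores. The only bound is logical: from 0 up to the approximately 100 subjects of Section 5.1.

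**The case against.** **The strict sign may be a PDF artefact.** Comparison signs come out in several forms in the extracted text, and a lost underline would turn ≥ into >. If both signs were misread, there would be no conflict. Against this, ≥ survives elsewhere, for example in Sections 1.1.2, 5.2 and 8.3, and the strict sign appears in two separate sections. The text as available does conflict, but the PDF should be checked first.

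**Section 8.2 may give only a sufficient condition.** It says who is eligible for discharge and does not say that a subject scoring 0 must be kept. That is literally true, and no passage contains an express instruction to hold at 0. But a threshold stated as above 0 naturally excludes 0, and Section 1.2 speaks of discharge itself, without the eligibility wording.

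**The consequences are small.** Only one score is in dispute, both rules withhold discharge below 0, and the stability and sedation safeguards apply regardless. This stands and limits the practical harm. It does not remove the need for a single value.

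**The upper bound of about 100 is unrealistic.** This also stands. It would require every subject to meet both subgroup conditions and to score exactly 0, whereas Section 1.1.2 expects significant withdrawal symptoms in this population. The bound is a logical limit, not an estimate.

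**Part of the body text may be absent.** Section 4.1 shows only a heading and the schematics are not visible, so a statement there cannot be excluded. This limits what can be said about precedence, but it does not reconcile the five statements that are present.

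**Conclusion.** The inconsistency holds, with high confidence on the text as given. One synopsis rule, stated for three settings, conflicts with Sections 1.2 and 8.2 at exactly one score, 0. The conclusion assumes that the > signs are printed that way in the PDF and that a threshold of above 0 is read in its ordinary sense as excluding 0.

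It should be fixed because sites act on this safety threshold. The sample size and primary analysis are not affected, and the number of subjects concerned is unknown.

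**What to change.** 1. Check the > signs in Sections 1.2 and 8.2 against the PDF. If either was printed as ≥, correct the reading and reassess.
2. If they stand, the sponsor and investigator should choose one threshold and state it identically in the three synopsis pathways, Section 1.2 and Section 8.2. Which value is right is for them to decide.
3. In the same amendment, check that Appendix 1, footnote g, fits the settled rule. It makes the 1-to-2-hour assessment time depend on the RASS score, whereas the text makes the 2-hour wait depend on COWS and recent release.

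The cost is wording only. Two sentences change if the synopsis threshold is kept, and three if the threshold in Sections 1.2 and 8.2 is kept, plus any edit to the footnote. Under Section 17 the amendment needs IRB/IEC approval before it is used. No new procedure is needed, because RASS is already assessed in this subgroup.
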